Milestone 1: NF loci (dACC or amygdala) must show higher activity during ESF-NF and higher FC with mPFC after NF training during the ESOM or ER tasks with effect sizes of $d \geq 0.4$.

Milestone 2: 20% of variance in psychological target's change (ETB, IAT) must be associated with amygdala or dACC to mPFC FC changes during the ESOM or ER tasks after NF.

If those milestones are met, during **the R33 phase**, 70 suicide attempting participants with pre-NF assessments will be randomized 1:1 to: NF or NF from a region that is not related to memory recall, labeled as "Unrelated-NF". Participants will be matched in sex, age, IQ, illness severity, suicide ideation, and abuse history if possible. Leveraging Bayesian methods to increase power, our aims and hypothesis (**H**) for the R33 phase are:

R33 Aim 1. Confirm target engagement in the NF versus the Unrelated-NF group.

H1.1: Right amygdala or dACC activity will be higher for active versus Unrelated-NF.

H1.2: Right amygdala or dACC – mPFC FC will be higher during self-processing and affect regulation tasks following active NF compared to Unrelated-NF training sessions.

R33 Aim 2. Test the relationship between neural and psychological targets' engagement and suicide ideation. H2.1: Lower affect dysregulation and abnormal self-processing behavior will follow active NF as compared to Unrelated-NF, mediated by amygdala or dACC to mPFC FC changes in self-processing and affect regulation tasks. H2.2: Higher amygdala or dACC to mPFC FC after NF will be associated with lower suicide ideation. H2.3: Affect dysregulation or abnormal self-processing behavioral changes will mediate the association between changes in FC and suicide ideation before versus after NF.

2. Background

Suicide is the 2nd leading cause of adolescent death in the U.S ²¹. Yet it is increasingly acknowledged that current evidence-based interventions for illnesses linked to suicide ideation and attempts underperform across the lifespan ^{1-7,22}.

3. Study Endpoints/Events/Outcomes

3.1 Primary Endpoint/Event/Outcome:

The primary outcome of the R61 stage will be the fMRI imaging results, behavioral tasks (IAT and EBT) and self-reported suicide ideation data. The DERS²³, RD¹²⁰ and the SPPA^{24,25} will provide self-report measures of affect dysregulation and abnormal self-processing. **The primary outcomes of the R33 stage** are similar as above but now include the C-SSRS⁹⁸ and SIQ²⁹ to test changes in suicide ideation and attempts

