Visit 1: Baseline	Visit 2: Scan day 1	Visit 3: Scan day 2	Visit 4: Post-NF	Visit 5: Approximately 1 Month later after Visit 4.	Additional visits as needed to complete pending tasks
KSADS. Children Depression Rating Scale-Revised (CDRS). Difficulty with Emotion Regulation Scale (DERS) ²³ . Self-Perception Profile for Participants (SPPA) ^{24,25} . Responses to Depression (RD) ⁴⁸ : rumination.	SIQ, BDI, DERS, SPPA, RD Medication, psychotherapy. Review 5 happy memories.	SIQ, BDI, DERS, SPPA, RD Review 5 happy memories.	SIQ, BDI, DERS, SPPA, RD.	SIQ, BDI, DERS, SPPA, RD Online	Anything pending
Columbia-Suicide Severity Rating Scale, C-SSRS, ⁴⁹ . Suicide Ideation Questionnaire, SIQ ²⁹ .	ESOM: 14 min ER: 13 min	NF Training: ESF_NF ~ 44.32 min	C-SSRS, CDRS	KSADS-COMP and C-SSRS	Anything pending
Beck Depression Inventory, BDI ²⁷ . Child Trauma Questionnaire, CTQ ²⁸	NF Training: ESF_NF~ 44.32 min	ESOM: 14 min ER: 13 min	IAT and ETB		Anything pending
Wechsler Abbreviated Scale for Intelligence, WASI ⁵⁰ . Edinburgh handedness inventory. Write/ discuss 5 happy memories.	30 min break	30 min break	Medication, psychotherapy	Medication and psychotherapy	Anything pending
Medication, psychotherapy, demographics, and puberty stage⁵¹.					Anything pending
Implicit Association Test (IAT): Abnormal Self-Processing Behavior ^{38,39} . Emotional Testing Battery (ETB): Affect and self-processing ⁴⁰ , or another similar test. Can be administered also before scanning on scan day 1 or after scanning on scan day 2.	Ease of recall rating. SIQ, BDI, DERS, SPPA, RD.	Medication, psychotherapy. Ease of recall rating. SIQ, BDI, DERS, SPPA, RD.		IAT and ETB	Anything pending

- Items from the KSADS, C-SSRS and Medication and psychotherapy forms will be shared with the IMM to confirm inclusion vs. exclusion of participants.

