Missing Data, Questionnaires and Tasks: Participants have the right to leave portions of tasks or instruments unfinished if they do not wish to answer the questions. **This is expected in any psychosocial research. This is not a protocol violation but a natural adaptation of the study procedures to the participant's wishes and status during the research.** All efforts will be made to complete items, questionnaires, and tasks while the study is active, and with the parents and the participant's consent. If participants are tired, they can either take some of the questionnaires and tasks at home, complete them remotely, or with the aid of researcher and staff personnel trained in clinical procedures for reconstruction of emotional and cognitive memories to finished questionnaires completed later. All efforts will be made to complete pending questionnaires and data via remote or in person contact with participants and their parents. [name], the PI, has experience with longitudinal research to recover missing data with the use of memory prompts and adequate clinical interviewing techniques like the ones employed for completing the K-SADS and the Mood Timeline which rely on the participant's memory of past symptoms and experiences. Questionnaires/tasks that need to be recovered will be administered and adapted to use clinical interviewing techniques that allow participants and their parents to recall the time period targeted by the study (**5-12 months**). **Modified instructions for recovering those questionnaires and procedures to be uploaded later.** **True missing data**, i.e., data that cannot be recovered or which is truly missing at the end of the data collection period, will be either statistically imputed (i.e., missing values will be estimated from available data or mean values will be used) or eliminated from analyses at the time of data analyses during the writing of papers.

Some of these items/questionnaires (ex, 18a and 18b and 18c) measure the same construct. We are aware of participant burden and in most cases will not use all of them. We would like approval or consideration for multiple measures to select from. In cases where there is a short form of the measure available, the short form will likely be used. We will also adapt the item used depending on the child's developmental stage (for example CDI for younger Participants and BDI for older Participants).

[figure not shown]

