R33 phase. We anticipate screening **~700** contacts for MRI eligibility over 3 years in the R33 phase. We expect that approximately **300 Participants may** perform baseline evaluations and pre-treatment tasks and to garner **~90** high quality scans for all NF sessions randomly assigned to active (**dACC or Right-Amygdala** depending on research phase) versus Unrelated-NF. **70** (minimal number for analysis) and complete pre and post NF-training phenotypical data and high-quality NF scans.

12. Local Recruitment Methods

12.1 Recruitment Process:

We will seek referrals from the Adolescent Inpatient Units at the University of Minnesota (U of M) MHealth Fairview, from the Washburn Children's and Fairview Clinics, the Minneapolis School Clinics, Children's Hospitals and the Emily Program as well as other mental health institutions in the Twin Cities area including Emergency Rooms. Clinicians within inpatient units will extend brief permission to contact forms to participants or their parents. Clinicians can also point out parents or participants to a Quick Response (QR) code that will trigger a permission to contact the used phone number to initiate the screening process. This method is particularly important to protect clinicians, participants and their family and the research staff from in person close contact in closed units to avoid contagion related to epidemics or other contagion agents.

Clinicians can inform research staff about specific patients that are suitable for research and research staff will then extend the permission to contact to the adolescent or their parents/caregivers. Clinicians will not explain the research in detail beyond what will be posted in the permission to contact forms or flyers. Instead, the contact forms or the **Quick Response (QR) code** will give researchers permission to call parents or Participants and explain the research over the phone and schedule an in-person or remote video call consent process. Additionally, individuals that might extend permission to contacts or use the Quick Response (QR) code include ER staff, doctors, therapists, social workers, pediatricians, or teachers. Both research staff and other referring personnel that extend permissions to contact or Quick Response (QR) code prompts will limit the effects of coercion by ensuring that patients and their caregivers understand that:

1st their decision to participate or not does not affect the quality or availability of care.

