H2.1: Lower affect dysregulation and abnormal self-processing behavior will follow active compared to Unrelated-NF, mediated by amygdala or dACC to mPFC FC changes in self-processing and affect regulation tasks. Bayesian mediation models will test the role of dACC or amygdala-mPFC FC changes on the relationship between NF and affect dysregulation and self-processing behaviors (ETB and IAT)⁶³. The outcome will be the behavioral change (ETB, IAT). The 1st linear model will be one used for H1.2, to test the relationship between the change in FC parameters and behaviors. For the 2nd linear model, the primary predictor will be the indicator term for the NF group, to establish the relationship between NF and behavioral change. Finally, in a 3rd model, the primary predictors will be indicator terms for the NF group, the change in FC parameters, and the interaction between them, to quantify the degree to which NF modifies the relationship between the change in FC parameters and behavioral change.

H2.2: Higher amygdala or dACC to mPFC FC after NF will be associated to lower suicide ideation. Bayesian linear model will use suicide ideation as the outcome, (C-SSRS, SIQ scores) and change in dACC or Amygdala-mPFC FC parameters in the ESOM and the ER tasks as the primary predictors.

H2.3: Affect dysregulation or abnormal self-processing behavioral changes will mediate the association between changes in FC and suicide ideation changes after versus before NF. Bayesian mediation models will test the direct and indirect effect of NF on suicide ideation, but this time we have two mediators: the neural targets and affect dysregulation or abnormal self-processing behavioral scores (ETB and IAT)^{63,64}. These mediators will interact, as we proposed in H2.1. We will fit a Bayesian mediation model with multiple mediators but this time with suicide ideation as the primary outcome, to quantify the direct and indirect effects of NF on suicide ideation change, with each of the change in FC parameters, affect regulation and self-processing behavior as potential mediators. We will fit another model that contains these mediation models as sub-models, i.e., a linear model with the NF indicator as primary predictor, each of the main effects for the change in FC and behavioral change, and an interaction term between the change in FC parameters and behavioral change.

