Bayesian Analyses in the R33 phase will use weakly informative priors using effects reported in the literature. Priors are a key strength of Bayesian models as they allow use of prior information to regularize models, e.g., using R61 phase results to adjust models in the R33 phase. This will boost statistical power since data from both phases will be used. Posterior distributions for model parameters will be constructed by combining priors with the likelihood function from the data. Markov Chain Monte Carlo (MCMC) procedures will be used to obtain samples from the posterior distributions for statistical inference. The Bayesian estimation will be implemented using custom R code in addition to the R package “BEST v0.4.0”^{65,66}.

Model selection and performance. In each of the Aims, we will start with baseline statistical model described above and improve the model by considering potential covariates that will allow the model to fit the data better and improve interpretability and predictive power. We will conduct a thorough search of potential statistical models that might improve on each of our baseline models. We will use residual analyses to assess how well each model fits the data and compute Bayes Factors to quantify quality of statistical models and use predictive cross-validation to assess the predictive capability of each model.

Data Integrity: The key scientific premise of this proposal is that improvement in emotion regulation and self-processing entail quantifiable changes in dACC and amygdala circuits. This proposal is aligned with the 2019 NIMH Strategic Plan 3.2: Develop ways to tailor new interventions to optimize outcomes and responds to the RFA MH-18-704: Development of Psychosocial Therapeutic and Preventive Interventions for Mental Disorders. Rigorous elements of the experimental design include: (a) using a specific threshold of

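### The missing-data rule permits mean filling of unrecovered outcome scores and leaves the choice among three methods to analysis time; one primary method should be named, with FC change in any imputation model

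*Combined protocol and SAP*

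**What the plan says.** Section 5.1 treats incomplete data as expected: "Participants have the right to leave portions of tasks or instruments unfinished if they do not wish to answer the questions". It describes efforts to recover missing material. What remains missing at the end of data collection "will be either statistically imputed (i.e., missing values will be estimated from available data or mean values will be used) or eliminated from analyses", and this is settled when the data are analysed and papers are drafted. That gives three methods, with no ranking and no statement of which mean is intended. Section 18 has no missing-data rule that would override this.

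The rule covers tasks and instruments in general, so it reaches the scores on which the main conclusions rest:

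- **Milestone 2 (Section 1):** 20% of the variance in change on the psychological targets ("ETB, IAT) must be associated with amygdala or dACC to mPFC FC changes during the ESOM or ER tasks after NF").
- **H2.1 (Section 18):** "The outcome will be the behavioral change (ETB, IAT").
- **H2.2 (Section 18):** "Bayesian linear model will use suicide ideation as the outcome, (C-SSRS, SIQ scores"), regressed on FC change.
- **H2.3 (Section 18):** suicide ideation as outcome, with FC change and ETB/IAT change as mediators.

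For R33, Section 18 plans MCMC, which "procedures will be used to obtain samples from the posterior distributions for statistical inference". Table 1 repeats several self-report scales across visits, for example "SIQ, BDI, DERS, SPPA, RD Review 5 happy memories" on a scan day.

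**The concern.** Estimating missing scores from available data can be sound if it carries the uncertainty forward. Replacing a whole outcome score with a mean does not do so. It adds records with no variation and no association with FC, and the analysis then counts them as real observations.

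Depending on which mean is used, the result is either too much certainty about the NF effect or an effect pulled towards zero. In Milestone 2, which is a condition for moving to R33, it lowers the R-squared that must reach 0.20. Because three methods are open until analysis, the choice could also follow the result.

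**Working it through.** **Inputs.** The Milestone 2 threshold is R-squared 0.20 (Section 1). R33 randomises 70 participants 1:1, so 35 per arm (Section 1). R61 has N=40, 20 per locus (Section 18, Power Analysis). The plan gives no missing rate, SD or effect size for ETB, IAT, SIQ or C-SSRS, so there is no figure of its own to reproduce. Assumed here: m = 5% or 10%, data missing completely at random, a true NF effect of 0.50 SD, and a true Milestone 2 R-squared of 0.25.

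**1. Change score filled with its arm mean.** Of n per arm, n(1-m) are observed. Filling adds nothing to the sum of squares, so the variance estimate falls to about (1-m)s². It is then divided by n instead of n(1-m).

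- Apparent SE² is proportional to (1-m)s²/n; correct SE² is proportional to s²/[n(1-m)].
- Ratio of SEs = (1-m).
- Coverage = 2Φ(1.96(1-m)) - 1.

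| m | Interval width relative to proper | Coverage |
|---|---|---|
| 5% | 0.95 | 93.7% |
| 10% | 0.90 | 92.2% |

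Simulation with 35 per arm and 40,000 runs agrees: at about 6% and 9% missing, coverage is 93.7% and 92.8%, and type I error is 6.3% and 7.2%. Using observed scores only, coverage is about 95%. If only the post score is filled with its arm mean, the loss is smaller: 94.1-94.7% at 5% and 93.3-94.1% at 10% (35 and 45 per arm; pre-post correlation 0.3 to 0.7 assumed).

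**2. Overall-mean filling.** Each arm mean becomes (1-m) × its own mean + m × the overall mean, so the difference becomes (1-m)Δ. A true 0.50 SD becomes 0.50 × 0.95 = 0.475 at 5% and 0.50 × 0.90 = 0.45 at 10%. Simulation gives 0.47 and 0.46 at about 6% and 9%.

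**3. Milestone 2 with behaviour change mean-filled.** The covariance with FC change and the outcome variance are both multiplied by (1-m), so R-squared is multiplied by (1-m)²/(1-m) = (1-m). From 0.25 it becomes 0.2375 at 5% and 0.225 at 10%. Chance that the sample R-squared reaches 0.20, n=40, 40,000 runs:

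| m | Observed pairs | Mean filling |
|---|---|---|
| 5% | 0.67 | 0.64 |
| 10% | 0.67 | 0.60 |

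The direction does not depend on these choices. With a true R-squared of 0.20 and 10% missing, the chance falls from 0.52 to 0.47 at n=20 and from 0.51 to 0.44 at n=40.

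**4. Multiple imputation that omits FC change.** Imputed values carry little or none of the FC association, so the covariance falls by about (1-m), while imputation restores the outcome variance. R-squared is then multiplied by about (1-m)². At m=10%, 0.25 × 0.81 = 0.2025, below the 0.225 from mean filling. Simulated chance of reaching 0.20 (n=40, 10% missing, true R-squared 0.25):

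| Method | Chance |
|---|---|
| Observed pairs | 0.66-0.68 |
| Mean filling | 0.59-0.60 |
| Imputation from arm, baseline and repeated self-reports only | 0.52 |
| The same with FC change added | 0.67 |

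**The case against.** The strongest reply is that little may ever be filled. Section 5.1 speaks of portions left unfinished and puts recovery first. Mean values could be read as prorating a few items from a person's own answers, which does much less harm and is not at issue. Section 11.1 aims for 70 in R33 ("minimal number for analysis) and complete pre and post NF-training phenotypical data and high-quality NF scans"). This stands as a limit on size: at 5% missing the distortion is modest. It does not remove the defect, because the text does not confine mean values to items, and a participant with good scans can still lack a usable IAT or ETB score.

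Overall-mean filling also shrinks the estimate and its standard error together, so a test of no effect stays roughly valid. That is correct; the estimate, the interval and the R-squared are what go wrong.

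A reader might infer three stronger points that the documents do not support:

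- **That about 20% of scores would be filled.** Section 29.1 expects 40 completers from about 50 with good scans in R61, and 72 from about 90 in R33. That is loss of whole participants, whom the completer targets suggest would be dropped.
- **That deletion is shown to bias the suicide-ideation results.** It could, if crisis-related loss differs by arm. But Section 14.1 allows re-enrolment after a crisis, and no loss rates by arm are given, so no size can be claimed.
- **That the two-arm coverage figures describe every model.** H2.2 regresses ideation on FC change with no stated arm contrast, and no coverage was worked out for it or for the H2.3 mediation models.

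**Conclusion.** The point holds as a conditional one. Mean filling of whole outcome scores is a permitted method and, where used, gives wrong intervals, shrunken effects or a lowered Milestone 2 R-squared, each by a factor of about (1-m). The direction and the formulas are firm for data missing completely at random. The sizes are illustrative: they rest on an assumed 5-10% missing, an assumed 0.50 SD effect and an assumed R-squared of 0.25, and they are small if analysis is mostly of complete cases. The absence of a primary method is plain from the text. This should be corrected before outcome data are seen; it does not by itself undermine the design.

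**What to change.** For outcome scores, delete the option of using mean values from Section 5.1 and name one primary method in Section 18 before outcome data are seen.

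- **R33:** sample missing outcomes within the MCMC models already planned, or use multiple imputation.
- **R61 Milestone 2:** use observed pairs, or multiple imputation. The planned Bayesian analyses are for R33, so they do not cover this step.
- **Any imputation model:** include every term of the analysis model. That means FC change, the NF-by-FC and FC-by-behaviour interactions where they are analysed, NF arm or locus, and baseline. Add the repeated SIQ, BDI, DERS, SPPA and RD scores as auxiliaries.
- **Sensitivity:** where imputation is primary, report the complete-case analysis alongside it.
- **Item prorating:** if wanted, define it separately.

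This concerns outcome scores only. It leaves the completer targets unchanged and does not impute FC. No new data are needed. The cost is SAP wording and some added programming, more for the mediation models. Intervals will be wider than arm-mean-filled ones by 1/(1-m): 1/0.95 = 1.05 and 1/0.90 = 1.11, so about 5-11% at 5-10% missing.
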